5.4 Withdrawal of Subjects from Study Treatment and/or Study

5.4.1 Permanent discontinuation of Durvalumab

An individual subject will not receive any further investigational product if any of the following occur in the subject in question:

1. Withdrawal of consent or lost to follow-up
2. Adverse event that, in the opinion of the investigator or the sponsor, contraindicates further dosing
3. Subject is determined to have met one or more of the exclusion criteria for study participation at study entry and continuing investigational therapy might constitute a safety risk
4. Pregnancy or intent to become pregnant
5. Any AE that meets criteria for discontinuation as defined in Section 6.0
6. Adverse event related to durvalumab that is Grade ≥ 3 , with the exception of toxicities that do not meet criteria for discontinuation as defined in Section 6.0
7. Grade ≥ 3 infusion reaction
8. Subject noncompliance that, in the opinion of the investigator or sponsor, warrants withdrawal; eg, refusal to adhere to scheduled visits

Initiation of alternative anticancer therapy including another investigational agent

Subjects who are permanently discontinued from further receipt of investigational product, regardless of the reason (withdrawal of consent, due to an AE, other), will be identified as having permanently discontinued treatment. Subjects who are permanently discontinued from receiving investigational product will be followed for safety, including the collection of any protocol-specified blood specimens, unless consent is withdrawn or the subject is lost to follow-up or enrolled in another clinical study. All subjects will be followed for survival.

5.4.2 Withdrawal of consent

If consent is withdrawn, the subject will not receive any further investigational product or further study observation.

If a patient withdraws consent, they will be specifically asked if they are withdrawing consent to:

- all further participation in the study including any further follow up (e.g., survival contact telephone calls)
- withdrawal of consent to the use of their study generated data
- withdrawal to the use of any samples

5.5 STUDY PROCEDURES

The Schedules of Assessments during the screening and treatment period is provided below.

Table 1. Schedule of study assessments: Screening and Treatment Period

| Visit (Assessments to be performed at the times stipulated in the table and as clinically required in the management of the subject.) | Screening | All assessments to be performed pre-infusion unless stated otherwise | | | | |
|--|------------------|--|---------------|---------------|---------------------------------|---|
| | | Baseline | Every 3 weeks | Pre-operative | Surgical resection _m | Postoperatively every 4 weeks for 12 cycles |
| Day | -28 to -1 | 1 | 22 | 36-49 | 36-69 | Day 1 of the week |
| Week | -4 to -1 | 1 | 4 | 6-7 | 6-10 | 11, 15, 19, 23, 27, 31, 35, 39, 43, 47, 51, 55 |
| | | | (±3 days) | | | |
| Written informed consent/assignment of subject identification number | X | | | | | |
| Preliminary eligibility fulfilment (investigator's opinion) | X | | | | | |
| Demography and history of tobacco and alcohol use | X | | | | | |
| Previous treatments for NSCLC | X | | | | | |
| Core Biopsy ^a | X | | | | | |
| Formal verification of eligibility criteria | X | | | | | |
| Medical and surgical history | X | | | | | |
| Hepatitis A antibody, hepatitis B surface antigen, hepatitis C antibody; HIV antibody | X | | | | | |

Table 1. Schedule of study assessments: Screening and Treatment Period

| Visit (Assessments to be performed at the times stipulated in the table and as clinically required in the management of the subject.) | Screening | All assessments to be performed pre-infusion unless stated otherwise | | | | |
|--|------------------|--|-------------------------|---------------|---------------------------------|---|
| | | Baseline | Every 3 weeks | Pre-operative | Surgical resection _m | Postoperatively every 4 weeks for 12 cycles |
| Day | -28 to -1 | 1 | 22 | 36-49 | 36-69 | Day 1 of the week |
| Week | -4 to -1 | 1 | 4 | 6-7 | 6-10 | 11, 15, 19, 23, 27, 31, 35, 39, 43, 47, 51, 55 |
| | | | (±3 days) | | | |
| Urine hCG or serum βhCG ^b | X | X | As clinically indicated | | | |
| ARM 1 Durvalumab administration (monotherapy) | | X | X | | | X ^k (monotherapy) |
| ARM 2 Durvalumab administration plus SBRT 8 Gy | | X ^l | | | | X ^k (monotherapy) |
| Physical examination ^c | X | X | X | X | | X |
| Vital signs (pre- during and post-infusion vital signs assessments) ^d | X | X | X | X | | X |
| Weight | X | X | X | X | | X |
| Electrocardiogram ^e | X | X | | | | |
| Adverse event/serious adverse event assessment | X | X | All visits | | | |
| Concomitant medications | X | X | All visits | | | |
| ECOG performance status | X | X | X | X | | X |

Table 1. Schedule of study assessments: Screening and Treatment Period

| Visit (Assessments to be performed at the times stipulated in the table and as clinically required in the management of the subject.) | Screening | All assessments to be performed pre-infusion unless stated otherwise | | | | |
|--|------------------|--|-------------------------|---------------|---------------------------------|---|
| | | Baseline | Every 3 weeks | Pre-operative | Surgical resection _m | Postoperatively every 4 weeks for 12 cycles |
| Day | -28 to -1 | 1 | 22 | 36-49 | 36-69 | Day 1 of the week |
| Week | -4 to -1 | 1 | 4 | 6-7 | 6-10 | 11, 15, 19, 23, 27, 31, 35, 39, 43, 47, 51, 55 |
| | | | (±3 days) | | | |
| Serum Chemistry (complete clin chem. panel including Liver enzymes) ^f | X | X | X | X | | X |
| Gamma glutamyltransferase | X | X | As clinically indicated | | | X |
| Thyroid function tests (TSH and fT3 and fT4) ^g | X | X | X | X | | X |
| Hematology ^f | X | X | X | X | | X |
| Urinalysis ^h | X | X | X | | | X |
| Coagulation parameters ⁱ | X | As clinically indicated | | | | X |
| Tumor assessment (CT/PET scan) ⁿ | X | | | X | | |
| Tumor assessment (Chest CT scan non-contrast) ^j | | | | | | X |

^a Tissue from core biopsies and resected specimens will be stored for future correlative studies . A research core biopsy for collection of tumor tissue is suggested but not mandatory.

^b Pre-menopausal female subjects of childbearing potential only.

^c Full physical examination at baseline; targeted physical examination at other timepoints.

^d Vital signs are temperature, blood pressure, pulse rate, and respiratory rate. Subjects will have their blood pressure and pulse measured before, during and after the infusion at the following times (based on a 60-minute infusion):

- At the beginning of the infusion (at 0 minutes)
- At 30 minutes during the infusion (±5 minutes)
- At the end of the infusion (at 60 minutes ±5 minutes)

- In the 1 hour observation period post-infusion: 30 and 60 minutes after the infusion (ie, 90 and 120 minutes from the start of the infusion) (± 5 minutes) – for the first infusion only and then for subsequent infusions as clinically indicated
If the infusion takes longer than 60 minutes then blood pressure and pulse measurements should be collected every 30 minutes (± 5 minutes) and as described above or more frequently if clinically indicated.

^e At screening and at Day 1-baseline, and as clinically indicated. Baseline and abnormal ECG at any time in triplicate, at screening in single. ECGs should be taken within an hour prior to the start of the infusion at Baseline C1D1.

^f If screening laboratory assessments are performed within 7 days prior to Day 1 they do not need to be repeated at Day 1. Results for safety bloods must be available and reviewed before commencing an infusion. Gamma glutamyltransferase (GGT) tested at Screening, Day 1 and as clinically indicated.

^g Free T3 and free T4 will only be measured if TSH is abnormal. They should also be measured if there is clinical suspicion of an adverse event related to the endocrine system.

^h Urinalysis performed at Screening, Day 1, Day 22, every 4 weeks during adjuvant durvalumab treatment, and as clinically indicated.

ⁱ Coagulation tests: prothrombin time, APTT and INR – only performed at Screening and as clinically indicated.

^j Post-operative CT scans are performed every 6 months for 2 years.

^k Subjects in Arm 1 and Arm 2 will receive adjuvant treatment with durvalumab monotherapy at 1.5 g every 4 weeks for 12 cycles starting 4-12 weeks postoperatively, following standard of care postoperative therapy, as required. Refer to Section 8.1.3 for subjects weighing ≤ 30 kg.

^l SBRT 8 Gy will be given on days 1, 2, and 3 only. On day 1, SBRT will be given prior to the durvalumab administration.

^m Surgical resection will take place 2 -6 weeks after the last dose of durvalumab. Tumor, adjacent normal lung, and lymph node specimens will be obtained from the surgical resection specimen, snap frozen.

ⁿ Standard of care CT/PET scans performed prior to obtaining informed consent and within 42 days prior to C1D1 may be used for screening.

Screening laboratory procedures performed within 7 days of Cycle 1 Day 1 (C1D1) do not need to be repeated on C1D1.

A 12-lead ECG will be recorded for all subjects on study days noted in Section 5.5, Schedule of Study Assessments. ECGs are required during Screening, at Baseline prior to starting study treatment on Cycle 1 Day 1 (C1D1), and at any other time point when clinically indicated. ECGs recorded during the screening period will be single tracing and ECGs recorded at Baseline prior to C1D1 will be obtained in triplicate (with 2-5 minute lag time between each). All 12-lead ECGs should be recorded while the subject is in the supine position. The same method of assessment should be used throughout the study. Twelve-lead ECGs will be obtained after the subject has been resting in a supine position for at least 5 minutes in each case. At Screening, a single ECG will be obtained on which QTcF must be <470 ms. In case of clinically significant ECG abnormalities, including a QTcF value >470 ms, 2 additional 12-lead ECGs should be obtained over a brief period (e.g., 30 minutes) to confirm the finding.

Vital signs (temperature, blood pressure, pulse rate, and respiratory rate) will be measured on study days noted in the Schedule of Assessments. On durvalumab treatment days, vital signs will be measured within an hour prior to start of durvalumab administration, at 30 minutes during the infusion (± 5 minutes), at the end of infusion ($+ 5$ minutes), and at 30 minutes (± 5 minutes) and 60 minutes (± 5 minutes) post-infusion. If the infusion takes longer than 60 minutes, then blood pressure and pulse

measurements should follow the principles described here, or more frequently if clinically indicated. For subsequent doses the 1-hour observation period will not be required unless a subject experiences an infusion-related reaction.

Table 2. Schedule of study procedures: follow-up for subjects who have completed or discontinued Durvalumab treatment

| Evaluation | Time Since Last Dose of Durvalumab | | | | | |
|--|---|------------------------|---|---|---|---|
| | Day (± 3) | Months (± 1 week) | | | | Every 6 Months for 2 years (± 2 weeks) |
| | 30 | 2 | 3 | 4 | 6 | |
| Physical examination ^a | X | | | | | |
| Vital signs (temperature, respiratory rate, blood pressure, pulse) | X | | | | | |
| Weight | X | | | | | |
| Urine hCG or serum β hCG | X | | | | | |
| AE/SAE assessment | X | X | X | | | |
| Concomitant medications | X | X | X | | | |
| ECOG performance status | X | X | X | | X | X |
| Adjuvant anti-cancer therapy, if required, as standard of care | X | X | X | X | X | X |
| Phone contact with subjects | | | | X | | |
| Hematology | X | X | X | | | |
| Serum chemistry | X | X | X | | | |
| Thyroid function tests (TSH, and fT3 and fT4) ^b | X | | | | | |
| Tumour assessment (non-contrast Chest CT scan) | Tumour assessments should be performed every 6 months for 2 years | | | | | |

^a Full physical exam

^b Free T3 and free T4 will only be measured if TSH is abnormal. They should also be measured if there is clinical suspicion of an adverse event related to the endocrine system.

The following clinical laboratory tests will be performed (see Schedule of study assessments and Schedule of procedures: follow-up) for the timepoints of each test):

- Coagulation parameters: Activated partial thromboplastin time and International normalised ratio to be assessed at baseline and as clinically indicated
- Pregnancy test (female subjects of childbearing potential only)
 - Urine human chorionic gonadotropin
 - Serum beta-human chorionic gonadotropin (at screening only)
- Thyroid Stimulating Hormone
 - free T3 and free T4 only if TSH is abnormal or if there is a clinical suspicion of an AE related to the endocrine system
- Other laboratory tests
 - Hepatitis A antibody, hepatitis B surface antigen, hepatitis C antibody
 - HIV antibody

Hematology Laboratory Tests

| | |
|---|-------------------------|
| Basophils | Mean corpuscular volume |
| Eosinophils | Monocytes |
| Hematocrit | Neutrophils |
| Hemoglobin | Platelet count |
| Lymphocytes | Red blood cell count |
| Mean corpuscular hemoglobin | Total white cell count |
| Mean corpuscular hemoglobin concentration | |

Clinical chemistry(serum or plasma) Laboratory Tests

| | |
|--|--|
| Albumin | Glucose |
| Alkaline phosphatase (ALP) | Lactate dehydrogenase |
| Alanine aminotransferase (ALT) | Lipase |
| Amylase | Magnesium |
| Aspartate aminotransferase (AST) | Potassium |
| Bicarbonate | Sodium |
| Calcium | Total bilirubin ^a |
| Chloride | Total protein |
| Creatinine | Urea or blood urea nitrogen, depending on local practice |
| Gamma glutamyltransferase ^b (GGT) | Uric acid |

^a If Total bilirubin is $\geq 2 \times \text{ULN}$ (and no evidence of Gilbert's syndrome) then fractionate into direct and indirect bilirubin

^b At baseline and as clinically indicated

Urinalysis Tests

| | |
|-----------|-----------------------|
| Bilirubin | pH |
| Blood | Protein |
| Glucose | Specific gravity |
| Ketones | Colour and appearance |

^a Microscopy should be used as appropriate to investigate white blood cells and use the high power field for red blood cells

Assessments for subjects who have completed durvalumab treatment or have discontinued durvalumab due to toxicity in the absence of confirmed progressive disease are provided in confirmed progressive disease are provided in Table 2 above.

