5.1 Treatment Plan

Patients with biopsy proven NSCLC clinical stages I (tumors > 2 cm), II, and IIIA will be randomly assigned to 2 preoperative cycles of the anti-PD-L-1 antibody durvalumab followed by surgical resection *or* non-ablative stereotactic radiotherapy given concurrently with the first cycle of the anti-PD-L1 antibody followed by an additional cycle of the antibody alone followed by surgical resection. In both arms of the trial, patients will receive adjuvant durvalumab every 4 weeks for a total of 12 cycles. Patients randomized to the antibody alone arm will receive two cycles of durvalumab at a dose of 1.12 g every three weeks. Patients in the radio-immunotherapy arm will also be treated with two cycles of durvalumab (1.12 g q 3 weeks) plus radiotherapy delivered in 3 daily fraction of 8Gy starting concurrently with the first cycle of durvalumab (see trial schema). This delivered non-ablative radiation dose of 24 Gy is equivalent to a biologically effective dose (BED) of 43.2Gy, which is significantly lower than the standard therapeutic dose for ablation of T1-T2 NSCLC (BED>100Gy). The objective is to induce immunogenic cell death, enhance antigen presentation and increase cytotoxic T lymphocyte activity without tumor ablation. This non-ablative dose of radiation is selected based on the results of studies by one of our co-investigators showing that the 8 Gy_x3 regimen resulted in significant immune modulation in preclinical models (24). A research core biopsy for the collection of tumor tissue is suggested but not mandatory. If a tissue biopsy has already been obtained for diagnostic purposes, a core biopsy may be performed for research purposes only to obtain tumor tissue. If a tissue biopsy has not been performed yet for diagnostic purposes, a core biopsy may be performed for diagnosis and tissue will be obtained for research purposes. Tissue from the preoperative core samples and from the resected surgical specimens will be stored for future correlative studies. Although PDL-1 expression is not required for eligibility, preoperative and post-operative tissue will be stored for future determination of PDL-1 expression. All patients will proceed to surgical resection 2-6 weeks after the second cycle of durvalumab regardless of local response assessment and provided that repeat imaging shows no evidence of systemic disease. Postoperative durvalumab will commence 4-12 weeks postoperatively at a fixed dose of 1.5 g every 4 weeks for 12 cycles. Patients receiving adjuvant chemotherapy may commence adjuvant monthly anti-PD-L1 after completing chemotherapy.

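### Table 1 fixes the first post-operative durvalumab infusion at study week 11, which is under 4 weeks after surgery for most surgery days that Section 5.1 allows when cycle 2 is on time

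*Combined protocol and SAP*

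**What the plan says.** **The fixed schedule.** Table 1 (Section 5.5) has one Day row and one Week row running from screening to the adjuvant phase. Baseline is day 1, week 1, and cycle 2 is day 22, week 4. The surgery column and the post-operative column then read "36-69 | Day 1 of the week" in the Day row. The Week row gives weeks 6-10 for surgery and "11, 15, 19, 23, 27, 31, 35, 39, 43, 47, 51, 55" for the infusions. The table headings say "Assessments to be performed at the times stipulated in the table", with an allowance for what clinical management requires, and "All assessments to be performed pre-infusion unless stated otherwise".

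**The rule counted from surgery.** Section 5.1 sets the surgery window: "All patients will proceed to surgical resection 2-6 weeks after the second cycle of durvalumab". Footnote m repeats it, counting from the last dose. Section 5.1 then sets the adjuvant start: "Postoperative durvalumab will commence 4-12 weeks postoperatively at a fixed dose of 1.5 g every 4 weeks for 12 cycles". Footnote k, attached to the post-operative dosing cells of both arms, agrees: "starting 4-12 weeks postoperatively, following standard of care postoperative therapy, as required".

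**The concern.** The post-operative weeks share a row with day 1 and day 22, so they count from first treatment. The surgery date can move by four weeks, yet the first infusion that follows it is printed as a single week. The last surgery week in the table is week 10 and the first adjuvant infusion is week 11, which leaves little room for a 4-week minimum.

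The stakes are operational. A site that books from the week row could infuse inside the protocol's own post-operative minimum. A site that follows footnote k would be off the printed weeks. Sections 4.1 and 10.2 foresee more than one institution, so the same conduct could be logged as a deviation at one site and not at another. Safety of the whole sequence is a secondary objective (Section 1.2), and Section 7.4 has a stopping rule on post-operative deaths. Unintended early dosing would make post-operative events harder to attribute.

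**Working it through.** **Inputs**

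| Input | Value | Source |
|---|---|---|
| Cycle 2 | day 22 | Table 1, Day row |
| Surgery | 14 to 42 days after the last pre-operative dose | Section 5.1, footnote m |
| First adjuvant infusion, fixed | day 1 of week 11 | Table 1 |
| First adjuvant infusion, rule | 28 to 84 days after surgery | Section 5.1, footnote k |
| Visit tolerance | ±3 days (which columns it covers is unclear in the text available) | Table 1 |

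**Step 1: the table's calendar.** Day 1 of week w is 7(w − 1) + 1. This gives day 22 for week 4 and day 36 for week 6, as printed. So week 11 is 7 × 10 + 1 = day 71, and week 55 is 7 × 54 + 1 = day 379. The series 11 + 4i, for i = 0 to 11, reproduces the twelve printed weeks.

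**Step 2: permitted surgery days with cycle 2 on time.** 22 + 14 = 36 and 22 + 42 = 64. Days 36 to 64 are 64 − 36 + 1 = 29 days.

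**Step 3: gap from surgery to day 71.** Gap = 71 − surgery day.

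| Surgery day | Gap (days) | At least 28? |
|---|---|---|
| 36 | 35 | yes |
| 43 | 28 | yes |
| 44 | 27 | no |
| 64 | 7 | no |

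Days 36 to 43 (8 days) comply. Days 44 to 64 (21 days) do not: 21/29 = 72% of permitted calendar days. No gap exceeds 84 days.

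**Step 4: does a ±3-day tolerance remove the conflict?**

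| Variant | Surgery days | Days short of 28 |
|---|---|---|
| Infusion 3 days late (day 74) | 36-64 | 18 of 29 |
| Infusion 3 days early (day 68) | 36-64 | 24 of 29 |
| Cycle 2 on day 19 | 33-61 | 18 of 29 |
| Cycle 2 on day 25 | 39-67 | 24 of 29 |

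It does not. On Table 1's own surgery range (days 36 to 69), 26 of 34 days are short, with a gap as low as 71 − 69 = 2 days.

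**Step 5: what the surgery-based rule implies.** The first infusion falls between 36 + 28 = day 64 (week 10) and 64 + 84 = day 148 (week 22). The twelfth is 11 × 28 = 308 days later, on days 372 to 456 (weeks 54 to 66). Both ranges are before any delay for chemotherapy.

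**Step 6: could any single week serve?** A fixed day D that suits every surgery day from 36 to 64 must satisfy 64 + 28 ≤ D ≤ 36 + 84, that is 92 to 120. Day 1 of weeks 14 to 18 qualifies; day 71 does not.

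**The case against.** The strongest reply is that the governing rule is in the same cell. Footnote k is on the dosing entries, Section 5.1 agrees with it, and no other section uses week 11. The headings about stipulated times concern assessments, and those move with the infusion. On this view the printed weeks are nominal labels, and early dosing would require a site to overlook both the footnote and the treatment plan. Most of this stands. It shows which text is intended and keeps the point minor. It does not make the printed weeks right: nothing labels them nominal, and week 11 suits only surgery by day 43.

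A reader might infer three stronger things that the documents do not support.

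- **That the table leaves out patients on adjuvant chemotherapy.** Section 5.1 says "Patients receiving adjuvant chemotherapy may commence adjuvant monthly anti-PD-L1 after completing chemotherapy". Footnote k covers the same ground by placing the start after any standard post-operative therapy, and Section 6.2.4 bars concurrent chemotherapy. No gap exists there.
- **That day 69 in the surgery column is always outside the window.** It is beyond day 64 for an on-time cycle 2. But Section 5.1 and footnote m count from the actual last dose, and Section 6.1 with Appendix B allows doses to be held for toxicity. If cycle 2 is given on day 27 (69 − 42) or later, day 69 is within 6 weeks. Such a hold makes the week 11 conflict worse: with cycle 2 on day 30 the earliest surgery is day 44, and no permitted surgery day then leaves 28 days before day 71.
- **That about 72% of patients would be dosed early.** The figure counts calendar days. The documents give no distribution of surgery dates, and a site following footnote k would dose correctly.

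**Conclusion.** The contradiction is real and minor. With cycle 2 on day 22, the printed week 11 meets the 4-week minimum for 8 of 29 permitted surgery days. For the other 21 it falls 7 to 27 days after surgery. The result rests on reading the post-operative weeks on the same calendar as the rest of the row, which the table's own day and week pairs support, and on an on-time cycle 2. It survives every ±3-day variant.

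The possible consequences are dosing inside the post-operative minimum and inconsistent coding of deviations; neither is shown to be likely. It would be wrong to infer a flaw in the design or in the primary analysis. The 4-to-12-week rule is stated consistently in Section 5.1 and footnote k. MPR is read from the resected specimen, before any adjuvant infusion, so the endpoint, alpha, power and sample size are untouched.

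**What to change.** Make two edits to Table 1.

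- **Last column:** replace weeks 11 to 55 with *infusion 1 at 4-12 weeks after surgery, then every 4 weeks for 12 infusions (see footnote k)*.
- **Surgery column:** replace the fixed days with *14-42 days after the actual last pre-operative dose (days 36-64 if given on day 22)*. Do not print a wider fixed range built from ±3 days, because a toxicity hold can exceed it.

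Footnote k needs no change. The cost is two column entries, with no extra patients, visits or analyses.

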8.1.3 Study drug preparation

For patients weighing > 30 kg a fixed dose of durvalumab at 1.12 g every 3 weeks for 2 cycles will be administered pre-operatively and 1.5 g every 4 weeks for 12 cycles post-operatively.

For patients ≤ 30 kg weight based dosing is required. For the 1.5 g dose a 20 mg/kg dose Q4W would be used and for the 1.12 g dose a 15 mg/kg dose Q3W would be used.

Preparation of durvalumab doses for administration with an IV bag

The dose of durvalumab for administration will be prepared using aseptic technique. Total time from needle puncture of the durvalumab vial to the start of administration should not exceed:

- 24 hours at 2°C to 8°C (36°F to 46°F)
- 4 hours at room temperature

If in-use storage time exceeds these limits, a new dose must be prepared from new vials. Infusion solutions must be allowed to equilibrate to room temperature prior to commencement of administration.

No incompatibilities between durvalumab and polyvinylchloride or polyolefin IV bags have been observed.

A dose of 1.5 g durvalumab for patients >30 kg will be administered using an IV bag containing 0.9% (w/v) saline with a final durvalumab concentration ranging from 1 to 20 mg/mL, and delivered through an IV administration set with a 0.2- or 0.22- μ m in-line filter. Add 30.0 mL of durvalumab (ie, 1.5 g of durvalumab) to the IV bag. The IV bag size should be selected such that the final concentration is within 1 to 20 mg/mL. Mix the bag by gently inverting to ensure homogeneity of the dose in the bag.

A dose of 1.12 g durvalumab for patients >30 kg will be administered using an IV bag containing 0.9% (w/v) saline with a final durvalumab concentration ranging from 1 to 20 mg/mL, and delivered through an IV administration set with a 0.2- or 0.22- μ m in-line filter. Add 22.4 mL of durvalumab (ie, 1.12 g of durvalumab) to the IV bag. The IV bag size should be selected such that the final concentration is within 1 to 20 mg/mL. Mix the bag by gently inverting to ensure homogeneity of the dose in the bag.

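### Table 1 marks two pre-operative durvalumab infusions in Arm 1 but one in Arm 2, contradicting sections 5.1 and 8.1.3; the passages must be reconciled

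*Combined protocol and SAP*

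**What the plan says.** **The schedule (section 5.5, Table 1).**
- The Arm 1 dosing row reads "ARM 1 Durvalumab administration (monotherapy) | | X | X": blank at screening, then marked on Day 1 and Day 22.
- The Arm 2 row, "ARM 2 Durvalumab administration plus SBRT 8 Gy", is marked on Day 1 (footnote l), blank on Day 22, and next marked in the post-operative column, where the entry is labelled monotherapy.
- Footnote l: "SBRT 8 Gy will be given on days 1, 2, and 3 only". It adds only that SBRT comes before the infusion on Day 1.
- Footnote m places surgery 2 to 6 "weeks after the last dose of durvalumab". The surgery column prints Days 36 to 69.

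**The treatment text.**
- Section 5.1 on Arm 2: "Patients in the radio-immunotherapy arm will also be treated with two cycles of durvalumab (1.12 g q 3 weeks) plus radiotherapy". It describes the sequence as radiotherapy with the first cycle, "followed by an additional cycle of the antibody alone followed by surgical resection". It times surgery for all patients from the second cycle.
- Section 8.1.3, with no distinction between arms: "a fixed dose of durvalumab at 1.12 g every 3 weeks for 2 cycles will be administered pre-operatively", for patients above 30 kg.
- The primary objective (1.1) refers to 2 cycles. The safety objective (1.2) and the third secondary aim (under 11.1.2) refer to 2 pre-operative cycles with and without radiation.

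**The concern.** Section 11.1.1 attributes the MPR difference, 15% in Arm 1 against 35% in Arm 2, to the addition of SBRT. That attribution needs the pre-operative antibody to be the same in both arms. The schedule table is the page that staff work from at each visit, and as printed it gives Arm 2 one infusion fewer before the primary endpoint is measured.

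A site that worked from the table would change two things at once between the arms: SBRT added and one antibody cycle removed. If some staff followed the table and others the text, Arm 2 would be a mixture. Section 11.2.1 compares the MPR proportions by arm and has no step that takes account of infusions received, so the discrepancy could pass into the primary result unremarked.

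**Working it through.** **1. Count of pre-operative infusions.**

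| Source | Arm 1 | Arm 2 |
|---|---|---|
| Table 1, marks before surgery | 2 (Days 1, 22) | 1 (Day 1) |
| Section 5.1 | 2 | 2 |
| Section 8.1.3 (no arm split) | 2 | 2 |
| Safety objective in 1.2 | 2 | 2 |

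**2. Can the Arm 2 row be read as SBRT only?** No. It also carries the post-operative durvalumab mark, so it is that arm's whole dosing row. Footnote l restricts the SBRT and footnote k covers adjuvant dosing. No other row or footnote schedules a Day 22 infusion for Arm 2.

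**3. Pre-operative dose for patients above 30 kg, at 1.12 g per cycle (8.1.3).**
- Table 1 as printed: Arm 1, 2 × 1.12 = 2.24 g; Arm 2, 1 × 1.12 = 1.12 g; ratio 1.12 / 2.24 = 0.50.
- Sections 5.1 and 8.1.3: 2.24 g in both arms; ratio 1.00.

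**4. Surgery window under the 2 to 6 week rule.**
- Last dose on Day 1: 1 + 14 = Day 15 to 1 + 42 = Day 43.
- Last dose on Day 22: 22 + 14 = Day 36 to 22 + 42 = Day 64, or Day 67 if the second dose uses the full 3-day allowance.
- Printed: Days 36 to 69.

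The printed lower bound matches a Day 22 last dose. The upper bound fits neither reading.

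**5. Stated power (11.1.1).** Inputs: 30 per arm, 0.15 against 0.35, one-sided 0.20 (z = 0.8416).
- Pooled proportion 0.25; null standard error √(2 × 0.25 × 0.75 / 30) = 0.1118.
- Alternative standard error √((0.15 × 0.85 + 0.35 × 0.65) / 30) = 0.1088.
- Power = Φ((0.20 − 0.8416 × 0.1118) / 0.1088) = 83.5%, against about 83% stated.

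The figure reproduces, and reconciling the table does not alter it.

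**6. Illustration only.** The documents give no MPR rate for a single cycle. Suppose every Arm 2 patient had one infusion and this lowered the Arm 2 rate. By the same formula, power would be 83% with no loss (35%), 71% at 30%, 55% at 25% and 37% at 20%. These rates are assumptions chosen to show scale; nothing in the documents supports any one of them.

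**The case against.** **The blank may not be real.** The text was read from PDF by a program. Elsewhere in this table, entries that seem to span several columns appear as one value followed by empty cells, for example the pregnancy-test and coagulation rows. A spanning mark in the Arm 2 row would look the same. Against that, the Arm 1 row directly above and the examination, vital-signs and weight rows directly below show Day 22 filled. A lost or merged cell cannot be ruled out, so this stands as a reason to check the original first.

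**The text is explicit.** Section 5.1 describes two cycles for Arm 2 more than once, and 8.1.3 and the objectives agree. Table 1 itself marks infusion-related vital signs on Day 22 without splitting by arm. A site would have to follow one cell over all of this. That stands: the harm is conditional, and a careful site may never meet it. It does not remove the contradiction.

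**Stronger readings that a reader might infer, and that the documents do not support:**
- *The design itself is confounded.* The treatment sections describe equal pre-operative antibody in both arms. Only conduct according to the table would break that.
- *Arm 2 gets half the drug.* This is true of the pre-operative phase only. Footnote k gives both arms the same 12 post-operative cycles.
- *Arm 2 would reach surgery with a third of the drug on board.* One can derive this from the half-life of about 21 days in the dose rationale if first-order decay is assumed, but no part of the documents links drug level at surgery to MPR.
- *The surgery window proves which dosing row is intended.* Its upper bound fails under both readings, so it is a separate discrepancy.

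**Conclusion.** The concern holds as an internal contradiction in the treatment schedule, provided that the blank cell is in the original PDF. Table 1 gives Arm 2 one pre-operative infusion where 5.1 and 8.1.3 give two.

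Its possible size is one infusion per affected Arm 2 patient, from none up to all 30, with half of Arm 1's pre-operative dose in each such patient. The documents offer no basis for saying how many, if any, would be affected. Where it happened, the MPR comparison would reflect SBRT together with a shorter antibody course. The direction of bias is not established: less antibody might plausibly dilute an SBRT effect, but no data in the documents show this.

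The power statement and the planned analyses are unaffected. It still deserves correction, because it concerns the number of study-drug infusions in one randomised arm before the primary endpoint.

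**What to change.** 1. Check the Day 22 cell of the Arm 2 row against the original PDF.
2. If it is blank there, reconcile that row with 5.1 and 8.1.3, so that the number and days of pre-operative infusions for each arm are stated identically throughout. This review takes no position on which schedule is right.
3. Give durvalumab and SBRT separate rows in Table 1, each with its own marks, so that a limit on one cannot be read as a limit on the other.
4. Reconcile the printed surgery days with the 2 to 6 week rule in 5.1 and footnote m.
5. Notify sites of the reconciled schedule.

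The cost is a table correction in an amendment and a site memo. Section 10.1 already provides for capture of all treatment data, so no new data item is needed, and the infusions actually given can be tabulated by arm beside the MPR result. Sample size, power and tests stay as written.
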